6.1 ANALYSIS POPULATIONS

The intent-to-treat (ITT) population will consist of all patients enrolled after implementation of Protocol Version 4 who received any study treatment. Randomized patients who receive incorrect therapy from that intended will be summarized in the group according to their planned randomized treatment. The ITT population will be the primary population for all analyses of primary and secondary efficacy variables.

The safety population for the trial will consist of all patients who enroll after implementation of Version 4 of the protocol and also receive any study treatment. The safety population will be the primary population for all safety analyses. For the purpose of all safety analyses, it will be assessed whether patients received a treatment different from the one they were randomized to at any time during the course of the study. In case the number and duration of such “treatment switches” warrants it, the safety population may be redefined by reallocating individual patients to the treatment actually received, as opposed to which treatment they were randomized to.

The PK population will include all patients randomized after implementation of Protocol Version 4 who received at least one dose, and had sufficient sampling to permit PK evaluation.

6.2 DETERMINATION OF SAMPLE SIZE

The planned sample size is adequate to capture meaningful clinical decline on both the TFC and cUHDRS and was estimated on the basis of data available from non-interventional studies (TRACK-HD, COHORT, ENROLL-HD) and a randomized placebo-controlled study (2CARE). Based on these data, using the anticipated trial population, a meta-analysis for the change from baseline at 24 months in TFC score suggested a natural decline of 1.36 points and a corresponding pooled standard deviation of 1.78. A conservative treatment discontinuation rate at Week 101 for patients receiving placebo or active is assumed to be 20% and 15%, respectively. Using these assumptions, the simulation described below was performed to estimate the sample size.

Description of Simulations to Derive the Sample Size

The design used for the simulation was simplified to consider only 2 treatment arms (placebo and active) and 2 postbaseline timepoints (Week 49 and Week 101). These simplifications are justifiable given that:

- The overall alpha level 5% will be split to 2.5%, such that each active treatment will be tested against placebo independently. Within each testing chain, a hierarchical procedure will be used to test the primary endpoint and secondary endpoints (see Section 6.3).
- The difference on the derived sample size for considering more than two postbaseline timepoints would be minimal.

The following algorithm was run and repeated 500,000 times:

1. Generate change from baseline values in TFC at Week 49 and Week 101 for N active patients according to the following bivariate normal distribution:

$$\begin{pmatrix} y_{wk49} \\ y_{wk101} \end{pmatrix} = N \left(\mu = \begin{pmatrix} 0.47 \\ 0.82 \end{pmatrix}, \sum = \begin{pmatrix} 1.56^2 & 1.8 \\ 1.8 & 1.78^2 \end{pmatrix} \right)$$

where y_{wk49} and y_{wk101} is the change from baseline in TFC, respectively, at Week 49 and Week 101, μ is the assumed true change at those two timepoints, and Σ is the variance-covariance matrix. Subsequently:

- set to missing, due to study drug-related (SDR) reasons, both values at Week 49 and Week 101 for 5% of the N patients. Set to missing, due to non-study drug-related (NSDR) reasons, both values at Week 49 and Week 101 for additional 2.5% of the N active patients.
- set to missing, due to SDR reasons, only the value at Week 101 for additional 5% of the N active patients. Set to missing, due to NSDR reasons, only the value at Week 101 for additional 2.5% of the N active patients.

2. Generate change from baseline values in TFC at Week 49 and Week 101 for N placebo patients according to the following bivariate normal distribution:

$$\begin{pmatrix} y_{wk49} \\ y_{wk101} \end{pmatrix} = N \left(\mu = \begin{pmatrix} 0.79 \\ 1.36 \end{pmatrix}, \Sigma = \begin{pmatrix} 1.56^2 & 1.8 \\ 1.8 & 1.78^2 \end{pmatrix} \right)$$

where y_{wk49} and y_{wk101} is the change from baseline in TFC, respectively, at Week 49 and Week 101, μ is the assumed true change at those two timepoints, and Σ is the variance-covariance matrix. Subsequently:

- set to missing both values at Week 49 and Week 101 for 10% of the N placebo patients
- set to missing only the value at Week 101 for additional 10% of the N placebo patients

Given how missing data will be imputed, it is not relevant to differentiate missing data into SDR versus NSDR reasons for placebo patients.

3. Apply multiple imputations and derive 20 complete datasets. Missing data on placebo patients were imputed from the placebo arm. Missing data on active patients, depending on if due to NSDR or SDR reasons, were imputed respectively from the active or the placebo arm.

4. Use a t-test to compare active versus placebo at Week 101 for each completed dataset and pool the result (Rubin 1987) to derive an estimate of the treatment effect, including a p-value.

Across the 500,000 simulations, the power achieved, with the N patients per arm was calculated by dividing the number of times the p-value (in above Step 4) was below 2.5%

by 500,000. The above procedure was repeated by only changing the N until the calculated power was close to 80%.

It was estimated that 267 patients per arm will provide approximately 80% power, at a two-sided $\alpha = 0.025$ level, to detect a 40% slowing of clinical decline for RO7234292 as compared with placebo at 101 weeks. This treatment effect translates into an expected average decline of ~0.82 points at 101 weeks for the RO7234292 arms. The minimal detectable difference with these assumptions is ~0.38 points.

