Note: The primary efficacy endpoint for the U.S. FDA will be change from baseline in the TFC score at Week 101. TFC will be analyzed the same way as the cUHDRS.

The primary efficacy analysis for this study will compare each active treatment arm, RO7234292 Q8W and RO7234292 Q16W, against the placebo arm. To account for the multiple comparison, an appropriate procedure will be used to maintain the overall two-sided type I error at 5% (details will be given in the SAP).

The analysis of the primary endpoint will be performed by means of analysis of covariance (ANCOVA). The model will include the corresponding endpoint baseline score, CAG repeat length, baseline CAP score, and treatment as covariates; the final list of covariates will be defined in the SAP. On the basis of this analysis, least squares mean for the treatment differences at Week 101 and corresponding 95% CIs will be derived.

The robustness of the primary method of estimation described above may be explored by alternative sensitivity estimators based on varying assumptions underlying the multiple imputation strategy. These sensitivity analyses will be described in the SAP.

Determination of Sample Size

The planned sample size is adequate to capture meaningful clinical decline on both the TFC and cUHDRS and was estimated on the basis of data available from non-interventional studies (TRACK-HD, COHORT, ENROLL-HD) and a randomized placebo-controlled study (2CARE). Based on these data, using the anticipated trial population, a meta-analysis for the change from baseline at 24 months in TFC score suggested a natural decline of 1.36 points and a corresponding pooled standard deviation of 1.78. A conservative treatment discontinuation rate at Week 101 for patients receiving placebo or active is assumed to be 20% and 15%, respectively. Using these assumptions, the simulation described in the protocol was performed to estimate the sample size.

It was estimated that 267 patients per arm will provide approximately 80% power, at a two-sided $\alpha = 0.025$ level, to detect a 40% slowing of clinical decline for RO7234292 as compared with placebo at 101 weeks. This treatment effect translates into an expected average decline of ~ 0.82 points at 101 weeks for the RO7234292 arms. The minimal detectable difference with these assumptions is ~ 0.38 points.

Optional Interim Analyses

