3. STUDY DESIGN

3.1 DESCRIPTION OF THE STUDY

3.1.1 Overview of Study Design

Study BN40423 is a Phase III, randomized, placebo-controlled, double-blind, multicenter clinical study to evaluate the efficacy, safety, PK, and biomarker effects of intrathecally administered RO7234292 in patients with manifest HD.

Effective 22 March 2021, no further study treatment will be administered in this study. Patients on the study will continue to be followed for safety and efficacy outcomes until study completion (see Section 3.1.1.1, [Appendix 1a](#), and [Appendix 1b](#)).

Prospective patients will undergo screening assessments during a 4-week screening period. A maximum of one re-screening will be allowed within 8 weeks of the initial screening failure for patients who fail the initial screening (see Section 4.5.1). If re-screening is required, the CAG repeat length testing from the initial screening does not need to be repeated (historical values prior to screening will not be accepted). The screening MRI and viral serology from the initial screening, including from other Roche RO7234292 studies, may be acceptable as part of the re-screening assessments if performed within 12 weeks of the baseline visit.

Upon completion of the screening period, eligible patients will be randomly allocated in a 1:1:1 ratio to receive RO7234292 Q8W (RO7234292 Q8W arm), RO7234292 Q16W (RO7234292 Q16W arm), or placebo Q8W (placebo arm) by IT injection, as described in [Table 1](#). To maintain the study blind and integrity, patients in the RO7234292 Q16W arm will also receive placebo (i.e., alternating doses of active drug and placebo).

Table 1 Treatment Regimens after Implementation of Protocol Version 4

Arm	Treatment Regimen
RO7234292 Q8W arm	RO7234292 loading dose: 120 mg at Days 1 and 29 (2 doses) RO7234292: 120 mg Q8W from Week 13 to Week 93 (11 doses)
RO7234292 Q16W arm	RO7234292 loading dose: 120 mg at Days 1 and 29 (2 doses) RO7234292: 120 mg Q16W from Week 21 to Week 85 (5 doses) Placebo: Q16W from Week 13 to Week 93 (6 doses)
Placebo arm	Placebo: at Days 1 and 29 (2 doses) and Q8W from Week 13 to Week 93 (11 doses)

Q8W =every 8 weeks; Q16W =every 16 weeks.

Note: Effective 22 March 2021, no further study treatment will be administered in this study.

During scheduled clinic visits, patients will undergo safety and tolerability evaluations that include neurologic examinations, vital signs, ECGs, clinical laboratory tests, MoCA,

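### The ~80% power in Section 6.2 and the synopsis belongs to the full-dosing design and no longer describes the Week 101 comparison that Version 6 runs after stopping all treatment

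*Protocol*

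**What the plan says.** Section 6.2 sizes the trial on TFC. For 24 months the pooled natural-history data "suggested a natural decline of 1.36 points and a corresponding pooled standard deviation of 1.78". A 40% slowing gives 0.82 points of decline on active, a difference of 0.54. The error rate is divided between the two active arms: "The overall alpha level 5% will be split to 2.5%, such that each active treatment will be tested against placebo independently". On discontinuation: "A conservative treatment discontinuation rate at Week 101 for patients receiving placebo or active is assumed to be 20% and 15%, respectively". A two-visit simulation (Weeks 49 and 101) was repeated over N "until the calculated power was close to 80" percent, giving 267 per arm and a minimal detectable difference of about 0.38. Section 6.2 states the result as: "It was estimated that 267 patients per arm will provide approximately 80% power, at a two-sided $\alpha = 0.025$ level, to detect a 40% slowing". The synopsis repeats the result: "It was estimated that 267 patients per arm will provide approximately 80% power".

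Table 1 in Section 3.1.1 plans injections to Week 93 in every arm. The last active dose is at Week 93 in the Q8W arm and at Week 85 in the Q16W arm, whose Week 93 injection is placebo. The same section then says: "Effective 22 March 2021, no further study treatment will be administered in this study". Section 3.1.1.1 and Appendix 1b move everyone to the early-termination schedule and provide for patients who have not yet had their Week 53 or Week 69 visit. Section 6 keeps the primary efficacy analysis at the end of the study.

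**The concern.** The design that was sized compares arms dosed almost to Week 101. The comparison now run is between arms that all stopped on one calendar date, some patients before Week 53. The power, discontinuation rates and minimal detectable difference are nevertheless still presented as properties of the Week 101 comparison.

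Elsewhere the amendment was carried through. Section 3.2 gives the old study length and the new one side by side, and Table 1 and Figures 1 and 2 carry a note on the stop. Section 6.2 carries none. The protocol itself ties interpretability to exposure: Section 4.6 warns that too many withdrawals, treatment discontinuation included, can make the results uninterpretable, and Section 3.3.1 argues that a shorter treatment period would need a much larger sample.

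Patients are still followed to Week 101 for the primary endpoint. A non-significant result read against a stated 80% power would count as fair evidence against a 40% slowing under full dosing. The amended design is not shown to support that reading.

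**Working it through.** **Inputs (Section 6.2).** 267 per arm; two-sided 0.025. TFC change at Weeks 49 and 101: placebo means 0.79 and 1.36, active means 0.47 and 0.82, so differences of 0.32 and 0.54. SDs 1.56 and 1.78, covariance 1.8. Missing on active: 5% drug-related plus 2.5% not drug-related at both visits, and the same again at Week 101 only. Missing on placebo: 10% at both visits and a further 10% at Week 101 only. 20 imputations, Rubin pooling, t-test.

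**Step 1: reproduce the stated figures.** Rerunning that algorithm gave 80.2% (3,000 replicates) and 79.6% (4,000 replicates), against about 80% stated. For the minimal detectable difference, 80% of 267 is 214 and 85% is 227, and 2.241 × 1.78 × √(1/214 + 1/227) = 0.380. Both figures reproduce.

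**Step 2: complete-data reference.** SE = 1.78 × √(2/267) = 0.154. Power is Φ(difference/SE − 2.241). For 0.54: Φ(3.505 − 2.241) = 90%. The smallest difference that keeps 80% is (2.241 + 0.842) × 0.154 = 0.475, which is 88% of 0.54.

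**Step 3: off-treatment values used.** Assumption: benefit accrues along the plan's own means, from 0 to 0.32 at Week 49 and 0.54 at Week 101, and is then held with parallel decline once accrual ends. Between Weeks 49 and 101 the difference is 0.32 + 0.22 × (week − 49)/52.

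| Accrual ends | Week 101 difference | Power, complete data | Power, plan's missing rates |
|---|---|---|---|
| Week 49 | 0.320 | 43% | 32% |
| Week 69 | 0.405 | 65% | 53% |
| Week 85 | 0.472 | 80% | 67% |
| Full effect | 0.540 | 90% | 80% |

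The two power columns have different baselines (90% and 80%), so a loss should be read within a column.

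Stopping on a calendar date spreads the weeks on treatment. With complete data and stop weeks spread evenly:

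- Weeks 5–101: mean difference 0.314, power about 42%.
- Weeks 25–101: mean difference 0.370, power about 56%.
- Weeks 45–101: mean difference 0.421, power about 69%.

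A common end of accrual would have to fall at about 49 + 52 × (0.475 − 0.32)/0.22 = Week 86 for complete-data power to stay at 80%.

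**Step 4: off-treatment values dropped and imputed as if on drug.** Section 6.6.1 applies this rule to discontinuations that are not drug-related. The target stays at 0.54; the loss comes from imputation. Simulation with Week 101 values removed in both arms, imputed from the same arm using Week 49, and nothing else missing (700 to 1,500 replicates):

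| Share of patients affected | Power |
|---|---|
| 30% | 82% |
| 40% | 75% |
| 50% | 69% |
| 75% | 40% |
| 90% | 16% |

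On this route 80% survives only if about a third of patients or fewer are affected.

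**The case against.** The strongest reply is that nothing in Section 6.2 is miscalculated. It explains how N was chosen, in the language of planning, and both figures reproduce. That stands, and a reader who inferred an arithmetic error or an under-sized original design would be wrong. It does not remove the point: the text says what 267 per arm will provide at Week 101, and nothing marks it as superseded.

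A reader might also infer that power has fallen to some particular low value. The protocol does not support that, for four reasons:

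- Weeks on treatment at the stop are not given. If most patients were late in dosing, the loss could be close to nil.
- Section 6.6.1 has two routes and does not say which applies to a sponsor-wide stop. Step 3 covers only one of them.
- The plan's missing rates treat discontinuation as missing data, whereas Version 6 recalls patients at Week 101. Adding those rates to a truncated effect is pessimistic.
- The end of accrual need not be the stop date. Section 1.3 reports a longer than expected effect on CSF mHTT, and Section 3.3.1 cites an animal model in which benefit outlasted target recovery. If benefit faded instead, power would be lower than Step 3 shows.

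Finally, the stop and the unfavourable trends are reported openly, and treatment differences will come with 95% confidence intervals. This limits the harm and is the right basis for reading the result. It does not justify leaving an unqualified 80% beside it.

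**Conclusion.** The point holds as one of stale labelling. The 80% power, the 15%/20% discontinuation and the ~0.38 are correct for the full-dosing design. They are not shown to apply to the Week 101 comparison after 22 March 2021.

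The size can be given only as a range. With off-treatment values used, accrued benefit held and complete data, power runs from about 43% (accrual ending at Week 49) to about 80% (Week 85), against 90% for the full effect, and about 42% to 69% over the spreads of stop weeks examined. With the plan's missing rates it is about 32% to 67% over the same accrual weeks, against 80%. With off-treatment values imputed as if on drug, it is about 82% at 30% affected and about 40% at 75%.

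All of this concerns TFC. The protocol gives no cUHDRS mean change or SD, so power for that endpoint cannot be checked. The 40% slowing is the plan's own assumption and not a forecast.

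**What to change.** In Section 6.2 and the synopsis:

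1. Label the 80% power, the 15%/20% discontinuation and the ~0.38 minimal detectable difference as planning figures for the full-dosing design, in the old-and-new style of Section 3.2.
2. State that they do not apply to the Week 101 comparison after the stop.
3. Rerun the existing simulation with the known distribution of weeks on treatment at the stop, under whichever estimand route applies. State the assumption about benefit after stopping, and give a range if needed.
4. State that a non-significant Week 101 result is to be read from its confidence interval and not as excluding a 40% slowing under full dosing.

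The cost is one rerun of a simulation that already exists and a few sentences. The stated power is likely to become less favourable, or to become a range. Enrolment and clinical management do not change.

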6.3 TESTING STRATEGY AND MULTIPLICITY ADJUSTMENT

The overall alpha level 5% will be split to 2.5% for testing each active treatment against placebo. A hierarchical approach will be used for multiple adjustments that accounts for multiple endpoints (the primary and secondary endpoints).

Within each testing chain (RO7234292 Q8W and RO7234292 Q16W), the endpoint will be tested only if the preceding endpoint is significant at the alpha level 2.5%. Details of the order for secondary endpoints will be detailed in the SAP.

6.4 SUMMARIES OF CONDUCT OF STUDY

The numbers of patients who enroll in the study, discontinue from the study, and complete the study will be summarized overall and by treatment arm. Reasons for premature study withdrawal will be listed and summarized. Enrollment and major protocol deviations will be listed and evaluated for their potential effects on the interpretation of study results.

6.5 SUMMARIES OF DEMOGRAPHIC AND BASELINE CHARACTERISTICS

Demographic and baseline characteristics (including age, sex, CAG repeat length, CAP, HD stage, education) will be summarized using means, standard deviations, medians, and ranges for continuous variables and proportions for categorical variables, as appropriate. Summaries will be presented overall and by treatment group.

6.6 EFFICACY ANALYSES

To ensure the treatment groups under comparison are concurrent and that treatment regimens are comparable across the entire dosing period of the 25-month study, for all efficacy analyses, patients enrolled prior to implementation of Protocol Version 4 will not be included and will be offered the option to enroll into Study BN40955 before reaching the primary endpoint assessment in the current study.

6.6.1 Estimands

Following the very recent estimand framework outlined in the ICH-E9 draft addendum (FDA 2017), the attributes of the estimand for the primary endpoint are defined as follows:

- Population: ITT population (see Section 6.1)
- Variable: Change from baseline in cUHDRS score at Week 101
 - Note: cUHDRS scale will be replaced by TFC scale for the FDA.
- Intercurrent events (ICEs):
 - Treatment discontinued for study drug–related reasons (e.g., treatment-related adverse event or lack of efficacy):
 - After treatment discontinuation, the actual off-treatment values will be used in the analysis.
 - Treatment discontinued for NSDR reasons (e.g., lost to follow-up):
 - After treatment discontinuation, imputed hypothetical values as if patients had continued receiving study drug will be used in the analysis. In this instance, any data collected after treatment discontinuation will not be included in the analysis.
- Population level summary: Difference in mean change from baseline at Week 101 between each active arm and the placebo arm

The primary estimand is a combination of a treatment-policy strategy and a hypothetical strategy (FDA 2017) to account for the different assumptions for each type of ICE.

The Sponsor will emphasize to investigators the importance of collecting data for the primary endpoint through Week 101, even if patients discontinue study drug but do not withdraw study consent, as well as the importance of providing detailed reasons for treatment discontinuation. The primary estimator, described by the statistical model in Section 6.6.2, will be applied on the dataset produced after multiple imputation of any missing value. In principle,

- missing data as well as off-treatment data from patients who discontinued treatment for NSDR reasons will be imputed from patients with available data from the same treatment arm collected while on treatment
- missing data from patients who discontinued treatment for SDR reasons will be imputed from:
 - patients with available data from the placebo arm collected either while on treatment or off treatment and
 - patients with available data from the same treatment arm collected while off treatment

Multiple imputation of missing data values will be performed as follows:

1. Imputation step: Missing data values will be imputed "m" times leading to "m" complete datasets.
2. Analysis step: Each of the resulting "m" datasets will be analyzed using the statistical model described in Section 6.6.2, which will provide an estimate of treatment difference.
3. Pooling step: The results from the "m" datasets will be combined (Rubin 1987) leading to an overall estimate of the treatment effect and associated 95% confidence intervals and p-values.

Full details of the algorithm for multiple imputation (e.g., which reference population to use for each missing data pattern, number of imputed datasets, method for imputation, etc.) will be provided in the SAP.

A supplementary estimand may be considered (and will be defined in the SAP).

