A pre-planned review of safety and efficacy data from Study BN40423, as well as available open-label data, was conducted by the BN40423 independent Data Monitoring Committee (iDMC). Following review of the data, the iDMC recommended that all dosing (120 mg Q8W and Q16W and placebo) in Study BN40423 be stopped. This iDMC recommendation was not based on any new emergent safety concerns, but on a totality of evidence indicating that the treatment arms demonstrated unfavorable safety and efficacy trends compared to the placebo arm over time. The iDMC also made a recommendation for the ongoing patients in the Study BN40423 to be followed for safety and efficacy outcomes as per protocol, without study drug administration.

As a result of iDMC's recommendation and Sponsor's decision, effective 22 March 2021, no further study treatment will be administered in this study. Patients on the study will continue to be followed for safety and efficacy outcomes until study completion (see Section 3.1.1.1, [Appendix 1a](#), and [Appendix 1b](#)).

The known potential risks related to lumbar punctures are elaborated, along with mitigation measures, in Section 5.1.

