C-SSRS, neuroimaging assessments (neurologic safety sequences), and a review of any adverse events including related concomitant medications, as detailed in [Appendix 1a](#). Patients in Japan must be monitored in the hospital setting for at least 24 hours after Day 1 study drug administration. Discharge will be determined at the discretion of the principal investigator.

In the case of a failed IT bolus dosing procedure *or a failed CSF collection procedure* (e.g., due to an inadequate establishment of access to the IT space), a second attempt may occur up to 7 days after the originally scheduled attempt. For this additional visit, safety and tolerability evaluations on the day of LP administration will be performed as detailed in [Appendix 1a](#) and [Appendix 1b](#), including neurological examination (predose and postdose, *or pre-procedure if no study treatment is being administered*), vital signs, and a review of adverse events and concomitant medication. If the second attempt occurs more than 3 days after the first attempt, local laboratory analysis of coagulation factors (INR and/or PT, aPTT) and platelets need to be conducted again and results reviewed prior to the LP attempt (see [Appendix 1a](#)).

During the treatment period, a telephone safety follow-up call will be conducted for the months in which no clinic visits are scheduled to check for any change in patient status (i.e., adverse events, concomitant medications) since the patient's last visit (see [Appendix 1a](#)). Where deemed appropriate, an unscheduled clinic visit should be arranged for safety follow-up; no dosing will occur at these unscheduled visits. A safety follow-up telephone call will also be conducted approximately 2 months after the last in-clinic visit at Week 101.

Effective 22 March 2021, all patients will discontinue study treatment and will no longer be able to enter the OLE study (BN40955) after completing this study.

[figure not shown]
For patients enrolled in Study BN40423 who discontinue study treatment prematurely, but do not withdraw consent for continued participation in the study, an ETT schedule will apply (Section 3.1.1.1).

An iDMC and independent Data Coordinating Center (iDCC) will be employed to monitor and evaluate patient safety throughout the study as well as to evaluate evidence of early efficacy (see Section 3.1.2).

The Sponsor may choose to conduct one or more interim analyses during the study (further details are given in Section [6.12](#)).

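### Section 6.6.1 does not classify the Sponsor-wide dosing stop of 22 March 2021, and its two intercurrent-event classes lead to very different Week 101 analyses

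*Protocol*

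**What the plan says.** **Estimand (Protocol Section 6.6.1).** There are two intercurrent events.

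- *Study drug-related (SDR) discontinuation*, with a treatment-related adverse event or lack of efficacy as examples. Observed off-treatment values are used. Only missing values are imputed, from two donor groups: "patients with available data from the placebo arm collected either while on treatment or off treatment and" off-treatment patients of the same arm.
- *Non-study drug-related (NSDR) discontinuation*, with loss to follow-up as the example. Hypothetical values under continued dosing are used: "In this instance, any data collected after treatment discontinuation will not be included in the analysis". Missing and off-treatment values "will be imputed from patients with available data from the same treatment arm collected while on treatment".

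**Conduct under Version 6.** Section 3.1.1 states: "Effective 22 March 2021, all patients will discontinue study treatment and will no longer be able to enter the OLE study". Section 1.3 adds: "Patients on the study will continue to be followed for safety and efficacy outcomes until study completion". Sections 3.1.1.1 and 4.6.1 keep visits at Weeks 53 and 69 (if not yet done) and Week 101, and name the primary and secondary endpoints as the purpose of the Week 53 and 69 visits. Patients who do not consent to Version 6 leave the study (Sections 4.2 and 4.6).

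**Unblinding.** The opening of Section 6 still has the Sponsor unblinded only after database lock, with the SAP final before then. Sections 3.1.2 and 4.2 unblind the Sponsor as a consequence of the stop.

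The Version 6 summary of changes lists no revision to any part of Section 6.

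**The concern.** The commonest reason for stopping treatment may now be a single Sponsor decision covering all arms, and the primary estimand does not say how to treat it. Each class can be argued. Section 1.3 reports unfavourable safety and efficacy trends in the active arms, which resembles the SDR example of lack of efficacy. The same section says the recommendation did not rest on new safety concerns, and placebo patients stopped as well, which points to NSDR.

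The choice is consequential. NSDR removes every post-stop outcome from the primary analysis and makes the Week 101 contrast depend on those who reached that visit on treatment. SDR keeps the post-stop outcomes and makes the contrast largely an off-treatment comparison. With the Sponsor unblinded, an unwritten choice can be made with treatment assignments known.

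**Working it through.** All figures are on the TFC scale, the only one for which Section 6.2 gives a variance.

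**1. Inputs (Sections 6.2 and 6.3).** "suggested a natural decline of 1.36 points and a corresponding pooled standard deviation of 1.78"; active decline 0.82, so the difference is 1.36 − 0.82 = 0.54. Week 49 means are 0.79 (placebo) and 0.47 (active), SD 1.56, covariance 1.8. "The overall alpha level 5% will be split to 2.5% for testing each active treatment against placebo", so the critical value is 2.2414. The design simulation uses 20 imputations.

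**2. The plan's own figure.** "It was estimated that 267 patients per arm will provide approximately 80% power". Re-running the Section 6.2 algorithm (8,000 runs, 267 per arm) gives 0.781, within 2 points. The stated minimal detectable difference of about 0.38 is also reproduced (0.380 with 85% and 80% completers).

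**3. Who can have an on-treatment Week 101 value?** Week 101 falls 100 weeks after Day 1, so a visit before the stop needs Day 1 on or before 22 April 2019. If a patient who had the last scheduled dose (Week 93) before the stop counts as on treatment at Week 101, the cut-off becomes 17 June 2019. The protocol gives no enrolment dates for the Version 4 cohort, so the share f cannot be derived and a range is assumed.

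**4. Stop classed as NSDR.** As a hand approximation, suppose everyone has an on-treatment Week 49 value and a share f has Week 101:

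- ρ = 1.8 / (1.56 × 1.78) = 0.648, so ρ² = 0.420
- complete-data SE = 1.78 × √(2/267) = 0.154
- SE factor = √(ρ² + (1 − ρ²)/f)
- power = P(Z > 2.2414 − 0.54/SE)

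The simulation uses the plan's imputation scheme, 2,500 runs per scenario, with 60% to 90% of patients having an on-treatment Week 49 value.

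| f | donors per arm | SE factor (hand) | power (hand) | SE (simulated) | power (simulated) | fraction of missing information |
|---|---|---|---|---|---|---|
| 5% | 13 | 3.47 | 0.11 | 0.61–0.62 | about 0.07 | 0.92 |
| 10% | 27 | 2.49 | 0.20 | 0.41 | 0.14–0.15 | 0.84–0.85 |
| 20% | 53 | 1.82 | 0.38 | 0.29–0.30 | 0.29 | 0.71–0.73 |
| 40% | 107 | 1.37 | 0.63 | 0.22–0.23 | 0.49–0.60 | 0.48–0.54 |
| 100% | 267 | 1.00 | 0.90 | – | – | – |

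The simulated power is lower because the formula omits the cost of a finite number of imputations, the reduced degrees of freedom and the uncertainty of a regression fitted to few donors; some simulated patients also lack Week 49. The like-for-like reference is 0.90 (complete data, no dilution), not the design's 80%, which already includes dropout and SDR dilution.

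**5. Stop classed as SDR.** Assume 20% of Week 101 values are missing, Week 49 is observed for all, and the full 0.54 persists off treatment. The slope on Week 49 is 1.8 / 1.56² = 0.740. The part of the effect not carried by Week 49 is 0.54 − 0.740 × (0.79 − 0.47) = 0.303.

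- Placebo donors only: 0.54 − 0.20 × 0.303 = 0.48. Simulated 0.48, power 0.77.
- The protocol's donors, taken in equal mix: 0.54 − 0.20 × 0.303/2 = 0.51. Simulated 0.51, power 0.81, fraction of missing information 0.12.
- If only half the effect persists (true 0.27), the protocol's donors give 0.26, power 0.24. The low power reflects the smaller effect rather than the imputation.

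**The case against.** **It belongs in the SAP.** Section 6.6.1 introduces the donor rules as principles and leaves the algorithm, the reference population for each missing-data pattern and any supplementary estimand to the SAP. That stands for donor detail. It does not cover the intercurrent events and their strategies, which the protocol fixes itself.

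**SDR fits naturally.** The two classes are exhaustive, the SDR examples are open-ended, and the stated trends resemble lack of efficacy. This is a fair reading, but the protocol does not adopt it.

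**Power for benefit is the wrong yardstick** in a trial stopped for unfavourable trends. Fair, but the loss of precision applies equally to a difference in either direction.

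**The simulation is simplified.** It has one earlier time point, whereas on-treatment values at Weeks 69 and 85, where available, would help the imputation. This also stands; the power figures indicate size only.

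A reader might infer more than the documents support:

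- *On-treatment donors hardly exist.* No enrolment dates are given. At 40% the loss is substantial but not fatal.
- *Under SDR, active-arm gaps are filled from placebo.* Observed off-treatment values are used first, and same-arm off-treatment patients are donors too. After a trial-wide stop they should be numerous.
- *Post-stop safety follow-up is lost.* Safety analyses use the safety population (Sections 6.1 and 6.7) and do not depend on this estimand.

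**Conclusion.** The point holds as a gap in the primary estimand. Section 6.6.1 was not updated for the dosing stop and does not say which rule applies.

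Read as NSDR, it contradicts the purpose of the continued follow-up by excluding post-stop outcomes. It also reduces power for 0.54 TFC points from about 0.90 with complete data to between about 0.07 and 0.6, for assumed on-treatment shares of 5% to 40%. Read as SDR, the analysis works with little dilution, given the assumptions of 20% missing and a fully retained effect, but the quantity estimated is the effect of a truncated course.

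The documents do not support saying that both routes fail, or that the Week 101 contrast cannot be estimated. What they show is that the route is open while the blinding safeguard assumed in Section 6 no longer applies.

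**What to change.** 1. Add the Sponsor-wide stop of 22 March 2021 to Section 6.6.1 as its own intercurrent event, handled by treatment policy in all arms, so that observed post-stop Week 101 values enter the primary analysis.
2. Impute values missing after the stop, including those of patients who decline Version 6, from same-arm patients who also stopped.
3. Keep the SDR and NSDR rules for discontinuations before the stop, but state how NSDR cases are imputed if few same-arm patients have on-treatment Week 101 data. Step 1 does not solve this, because the on-treatment donor rule still applies to them.
4. Reconcile the unblinding text at the start of Section 6 with Sections 3.1.2 and 4.2, and record when the event's handling was fixed relative to Sponsor unblinding.

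An on-treatment supplementary estimand may be left to the SAP.

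The cost is protocol and SAP wording, with no new data. The downside is that the primary result must be described as the effect of a truncated course of treatment, not of the planned regimen to Week 101.
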